	
The Per-Protocol Population is defined as the subset of patients in the ITT who do not have any major protocol deviations that could affect the efficacy analyses of the double-blind data.
 
Inclusion in the Per-Protocol Population will be determined prior to unblinding the data and will be detailed in the statistical analysis plan.
 
The Open-label Safety Population is defined as the group of patients who receive at least 1 dose of study drug in the Open-label Phase. The Open-label Safety Population will be used to analyze all safety endpoints collected during the Open-label Phase, and during exposure to CR845 combining data from both the Double-blind and the Open-label Phases.
 
Safety Analyses
 
Safety data will be summarized descriptively. No inferential statistics are planned. Analyses of safety data will include summaries of treatment-emergent adverse events including Adverse Events of Special Interest (AESI), serious adverse events, and adverse events resulting in study drug discontinuation. Vital signs, chemistry and hematology data, ECG data will be presented by visit as applicable, in addition to change from baseline.
 
Efficacy Analyses (Double-blind Treatment Period)
 
All efficacy analyses will be conducted on the ITT Population. An analysis of the primary and secondary efficacy variables for the Per-Protocol Population will also be performed.
 
Primary Efficacy Endpoint
 
The primary efficacy endpoint is defined as the proportion of patients achieving at least a 3-point improvement from baseline with respect to the weekly mean of the daily 24-hour Worst Itching Intensity NRS score at Week 12 (Days 79-85) of the Double-blind Treatment Period. The weekly mean of the 24-hour Worst Itching Intensity NRS score will be defined as the sum of the daily Worst Itching Intensity NRS score reported during a specific week during the Double-blind Treatment Period (eg, Days 2 to 8, Days 9 to 15, Days 16 to 22, etc., Days 79 to 85) divided by the number of days with non-missing scores for that week. If the daily worst itching score is missing for >3 days during a specific week, the corresponding weekly mean worst itching score will be set to missing. The baseline score will be defined as the average of the daily 24-hour Worst Itching Intensity NRS scores collected over the Run-in Period, including pre-randomization assessments collected on Day 1.
 
In the primary efficacy analysis, missing NRS data will be imputed using a multiple imputation (MI) approach, assuming that patients who discontinue double-blind treatment early would have similar Worst

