 - b. Has a mean baseline Worst Itching Intensity NRS score >4 , defined as the average of all non-missing scores reported from the start of the 7-day Run-in Period up to and including the pre-randomization assessment on Day 1.

To be eligible for inclusion into the Open-label Extension Phase of the study, each patient will have to fulfill the additional following criteria at the time of entry into the Open-label Extension Phase:

11. Has received at least 30 doses of the planned 36 doses of study drug during the Double-blind Phase of this study;
12. Has a prescription dry body weight ≥ 40 kg;
13. Continues to meet inclusion criteria 1 through 7.

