A patient will be excluded from the Open-label Extension Phase of the study if any of the additional following criteria are met at the time of entry into the Open-label Extension Phase:

13. Completed the Double-blind Phase of this study but exhibited adverse events during the course of the Treatment Period that may preclude continued exposure to the study drug;
14. Was noncompliant with protocol procedures during the Double-blind Phase of this study which is indicative of an inability to follow protocol procedures;
15. Has developed a concomitant disease or any medical condition that, in the opinion of the Investigator, could pose undue risk to the patient, impede completion of the study procedures, or would compromise the validity of the study measurements.

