6.3 Removal of Patients from Therapy or Assessment

6.3.1 Discontinuation of Individual Patients

A patient may withdraw from the study at any time at his/her own request for any reason without prejudice to future medical care by the physician or at the institution.

A patient may be withdrawn at any time due to the following reasons:

1. At the discretion of the Investigator or the Sponsor for safety, behavioral, compliance, or administrative reasons;
2. If a patient misses 3 consecutive doses either on Week 11 or Week 12 of the Double-blind Treatment Period (these patients may still be eligible for the Open-label Phase at the discretion of the Investigator in consultation with the Sponsor).
3. If patient misses 6 consecutive doses at any time;
4. At the discretion of the Sponsor/Medical Monitor, if a patient receives a prohibited concomitant medication according to [Table 1](#).
5. Any patient who becomes pregnant during treatment must be withdrawn from the study (see Section [6.5.4.7](#)).

Whenever possible, withdrawal of a patient from study drug by the Investigator should be discussed with the Medical Monitor before the patient stops study drug.

If study drug is discontinued, regardless of the reason, an Early Termination Visit should be completed at the first dialysis after the last dose of study drug or, if not feasible during that timeframe, as soon as feasible. If at all possible, a monitored 2-week Discontinuation Period is to be completed after the Early Termination Visit in the Double-blind Phase.

Although a patient will not be obliged to give a reason for withdrawing prematurely, the Investigator must make a reasonable effort to obtain the reason while fully respecting the patient's rights. The reason(s) for termination and date of stopping study drug must be recorded on the electronic case report form (eCRF) and source documents.

If a patient discontinues early due to an adverse event, the event will be followed until resolution, the patient returns to baseline status, the condition stabilizes, or the patient is lost to follow-up.

A patient will be considered lost to follow-up when no response is received from the patient after at least 3 documented attempts to contact the patient over a minimum time of 2 weeks by the study site.

If the patient withdraws consent for disclosure of future information, the Sponsor may retain and continue to use any data collected before such a withdrawal of consent.

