8.5 Analysis Populations

The Enrolled Population is defined as the group of patients who sign informed consent.

The ITT Population is defined as the group of patients who are randomized to a treatment group.

The Double-blind Safety Population is defined as the group of randomized patients who received at least 1 dose of double-blind study drug during the Double-blind Treatment Period.

Following the intent-to-treat principle, patients in the ITT population will be analyzed according to their randomized treatment, regardless of the actual treatment received. Patients in the Double-blind Safety Population will be analyzed according to the actual treatment received. The Double-blind Safety Population will be used to analyze all safety endpoints collected during the Double-blind Phase, while the ITT Population will be used to analyze all efficacy endpoints collected during the Double-blind Phase.

The Per-Protocol Population is defined as the subset of patients in the ITT Population who do not have any major protocol deviations that could affect the efficacy analyses of the double-blind data. An analysis of the primary and secondary efficacy variables for the Per-Protocol Population will be performed.

Key exclusions from the Per-Protocol population include patients who:

- Received less than 80% of the planned study drug doses
- Had a mean baseline Worst Itching Intensity score ≤ 4.0
- Had a missing average 24-hour weekly Worst Itching NRS score for $\geq 25\%$ of study weeks
- Had significant amounts of restricted and prohibited medications (Section 6.4.9) based on medical review
- Received a different treatment than the treatment to which they were randomized

Inclusion in the Per-Protocol Population will be determined prior to unblinding the data.

The Open-label Safety Population is defined as the group of patients who receive at least 1 dose of study drug in the Open-label Phase. The Open-label Safety Population will be used to analyze all safety endpoints collected during the Open-label Phase, and during

exposure to CR845 combining data from both the Double-blind and the Open-label Phases.

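### The combined CR845-exposure safety analysis is run on patients who reached the open-label phase, so double-blind deaths on CR845, and nearly all double-blind adverse-event discontinuations on CR845, cannot appear in it

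*Protocol*

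**What the plan says.** Protocol Section 8.5 defines the set: "The Open-label Safety Population is defined as the group of patients who receive at least 1 dose of study drug in the Open-label Phase". The same section, and the Synopsis under Analysis Populations, give this set two jobs, the open-label safety data and safety across all CR845 exposure: "The Open-label Safety Population will be used to analyze all safety endpoints collected during the Open-label Phase, and during exposure to CR845 combining data" from the two phases.

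Entry to the open-label phase is conditional. Protocol Section 6.2.1, criterion 11, requires that the patient "Has received at least 30 doses of the planned 36 doses of study drug during the Double-blind Phase of this study". Section 6.2.2, exclusion 13, removes patients who finished the Double-blind Phase but "exhibited adverse events during the course of the Treatment Period that may preclude continued exposure to the study drug". Exclusion 15 removes patients with a newly developed condition that the Investigator thinks poses undue risk. There is one narrow route back: under Section 6.3.1, patients may be withdrawn for three consecutive missed doses in Week 11 or 12, and "these patients may still be eligible for the Open-label Phase at the discretion of the Investigator in consultation with the Sponsor".

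Double-blind safety is analysed on the Double-blind Safety Population, meaning everyone with at least one double-blind dose (protocol Section 8.5, SAP Section 4.3). Protocol Sections 8.1 and 8.8 leave the detail of the cross-phase analysis to the SAP. The supplied SAP covers the double-blind phase only, sends the extension to a separate document (Sections 1 and 2.2.2), and lists no all-CR845-exposed population in Section 4.

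**The concern.** The analysis is described as covering exposure to CR845 across both phases, but membership is decided by what happened during the first of them. A patient randomised to CR845 who dies or stops for an adverse event in the first 12 weeks was exposed to the drug, yet is in neither the numerator nor the denominator.

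Safety is a stated secondary objective (protocol Section 5.0), and Section 7.1 gives long-term safety information as the purpose of the open-label part. A reader of a combined-exposure table would expect it to include every patient exposed to CR845. As written, it leaves out the most serious early outcomes in the CR845 arm.

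**Working it through.** No figure in the plan is at issue, so the first check is a comparison of the rules.

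**1. Who is counted**

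| Patient | Exposed to CR845 | In the combined analysis | In the double-blind tables |
|---|---|---|---|
| CR845 arm, dies in the Double-blind Phase | Yes | No, always | Yes |
| CR845 arm, stops for an adverse event before 30 doses | Yes | No (criterion 11) | Yes |
| CR845 arm, stops for an adverse event after 30 doses | Yes | Rarely: criterion 11 is met, but the adverse-event and new-condition exclusions apply | Yes |
| CR845 arm, withdrawn for missed doses in Week 11 or 12 | Yes | Possibly (Section 6.3.1) | Yes |
| CR845 arm, declines to roll over | Yes | No | Yes |
| CR845 arm, rolls over | Yes | Yes, both phases | Yes |
| Placebo arm, rolls over | Yes, from Open-label Day 1 | Yes, all CR845 exposure | Yes, as placebo |

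At three doses a week, 30 doses take 30/3 = 10 weeks, so stopping before about the end of Week 10 rules a patient out on dose count alone.

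**2. Deaths that could not appear**

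Inputs: 4 deaths in 174 patients, all arms, over 8 weeks (protocol Section 4.2.2); 175 CR845 patients planned, up to 250 (Section 8.2).

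- Rate: 4/174 = 2.3%.
- Unscaled: 175 × 4/174 = 4.0 deaths.
- Scaled to 12 weeks at a constant rate: 4.0 × 12/8 = 6.0 deaths.
- With 250 CR845 patients: 5.7 unscaled, 8.6 scaled.

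The combined summary would contain none of them.

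**3. Time in which death was impossible**

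A CR845-arm patient who rolls over brings about 12 double-blind weeks that, by the entry rule, contain no death. Assume equal numbers roll over from each arm.

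- Full 52-week open-label follow-up: share of combined CR845 time = 12/(12 + 52 + 52) = 10.3%.
- Mean open-label follow-up of 26 weeks (assumed): 12/(12 + 26 + 26) = 18.8%.

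A death rate per person-year, the form SAP Section 9.2 uses for double-blind fatal events, would fall below the open-label rate by those shares.

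**4. Serious adverse events: direction not fixed**

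Take s = 27/129 = 20.9%, the Phase 2 proportion of CR845 patients with a treatment-emergent serious event (Section 4.2.2). Assume a share d of the CR845 arm does not enter the open-label phase, and that patients with a serious event are m times as likely not to enter. With q = d/(s·m + 1 − s), the double-blind proportion among CR845 patients who do enter is s(1 − m·q)/(1 − d).

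| d | m | Proportion among entrants |
|---|---|---|
| any | 1 | 20.9% |
| 10% | 2 | 19.4% |
| 20% | 2 | 17.5% |
| 20% | 3 | 15.1% |
| 30% | 3 | 10.9% |

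That covers double-blind events only. A crude percentage over all CR845 exposure can move the other way, because excluded patients have at most about 12 weeks of exposure. At a constant 21% per 8 weeks with full follow-up:

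- 12 weeks: 1 − 0.79^1.5 = about 30%. 52 weeks: 1 − 0.79^6.5 = about 78%.
- With d = 20% and m = 3, q = 0.2/(0.30 × 3 + 0.70) = 0.125. About 0.30 × 3 × 0.125/0.2 = 56% of the 35 non-entrants (20% of 175) had an event, and about 23% of the 140 entrants had one while double-blind.
- Entrants from the CR845 arm reach 1 − 0.77 × 0.22 = about 83% and former placebo patients about 78%, averaging about 81% of 280.
- Adding the 35: (280 × 0.81 + 35 × 0.56)/315 = about 78%.

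In that case the complete population shows a lower crude percentage than the restricted one.

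**The case against.** The strongest reply is that nothing is lost from the study. Every double-blind death, serious event and discontinuation on CR845 is tabulated on the Double-blind Safety Population by treatment received, with person-time rates for serious and fatal events (SAP Section 9.2) and death listings (Section 9.3). The placebo-controlled comparison is intact. This stands, and it confines the defect to one descriptive summary with no hypothesis test.

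Second, the open-label SAP was not available and may define an all-exposed set. That is possible, and the supplied SAP's silence reflects its scope. But the protocol states the rule twice, so a better definition elsewhere would contradict it and the protocol text would still need correcting.

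Third, following patients who enter an extension is a coherent question. It is, for open-label data. It does not answer the question about all exposure to CR845 that the protocol attaches to the same set.

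A reader might also infer that the combined summary keeps only survivors who tolerated the drug. The documents do not support that. Former placebo patients belong to the population too, and their CR845 exposure is counted in full from the first dose, including later stops and deaths. Open-label deaths and stops in the former CR845 arm are counted as well.

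**Conclusion.** The rule is wrong as written for deaths and discontinuations. The zero contribution of double-blind deaths on CR845 follows from the definitions and needs no assumption. The near-absence of double-blind adverse-event discontinuations follows from the entry criteria, apart from rare late stops that still pass them. The dilution of a person-time death rate also follows from the definitions; its 10% to 19% size rests on equal roll-over by arm and the two follow-up lengths shown.

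The overall size cannot be derived from the documents. The 4 to 6 deaths per 175 carry over an all-arm Phase 2 rate built on 4 events, all judged unrelated to study drug.

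Three stronger readings are tempting and should not be drawn:

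- That all combined rates are biased downward. For crude percentages of other adverse events the direction is uncertain, because follow-up differs.
- That adverse-event discontinuation would look about 30% lower. Assuming 8% discontinue in each phase and 140 per arm roll over gives (14 + 22)/(175 + 140) = 11.4% against 22/280 = 7.9%, but none of those inputs is in the documents.
- That this is the trial's overall safety summary. Neither the objectives nor the safety endpoints give it that status.

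**What to change.** In the Synopsis (Analysis Populations) and Section 8.5 of the protocol, limit the Open-label Safety Population to data collected in the open-label phase. Add an All CR845 Exposure Population: every patient who received at least one dose of CR845 in either phase, with time at risk starting at the first CR845 dose (Double-blind Day 1 for the CR845 arm, Open-label Day 1 for the placebo arm). Use it for the combined-exposure analysis, report exposure-adjusted rates beside percentages because follow-up is unequal, and carry the same definition into the open-label SAP, preferably before pooled results are seen.

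The entry criteria need no change, and no new data, visits or procedures are required. The cost is slightly more analysis work, and some pooled rates may become less favourable.

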3.0 List of Abbreviations

AESI	adverse event of special interest
ATC	Anatomical Therapeutic Chemical
CFR	Code of Federal Regulations
CI	confidence interval
CNS	central nervous system
ECG	electrocardiogram
eCRF	electronic case report form
ESA	erythropoiesis-stimulating agent
ESRD	end-stage renal disease
FDA	Food and Drug Administration
GCP	Good Clinical Practice
H	above the laboratory parameter's reference range
ICF	informed consent form
ICH	International Council for Harmonisation
IDMC	Independent Data Monitoring Committee
IL	interleukin
IND	Investigational New Drug
IRB	Institutional Review Board
ISF	Investigator Site File
IV	intravenous
IVRS/IWRS	interactive voice or web response system
KOR	kappa-opioid receptor
L	below the laboratory parameter's reference range
LS	least squares
MAR	missing at random
MCMC	Markov Chain Monte Carlo
MedDRA	Medical Dictionary for Regulatory Activities
MI	multiple imputation
MMRM	mixed effects model with repeated measures
MNAR	missing not at random
N	within the laboratory parameter's reference range
NRS	numerical rating scale
OOWS	Objective Opiate Withdrawal Scale
PRO	patient-reported outcome
SAE	serious adverse event
SAP	statistical analysis plan
SE	standard error
ShOWS	Short Opiate Withdrawal Scale
SOC	System Organ Class
TEAE	treatment-emergent adverse event
ULN	upper limit of normal

Abbreviations that occur only in tables or figures are defined within the appropriate table or figure.

4.0 Introduction

4.1 Background and Rationale

CR845 is a kappa-opioid receptor (KOR) agonist with a peripheral mechanism of action being developed by Cara Therapeutics, Inc. (designated as Cara Therapeutics or Sponsor in this protocol) as a novel therapeutic agent for the symptomatic relief of acute and chronic pain and pruritus.

Opioid receptors are involved in the modulation of itch and pain signals and consist of 3 subtypes: mu, kappa, and delta. These receptor subtypes are found in the central nervous system (CNS), in peripheral nervous system tissues, such as skin and viscera, and in the immune system (see [Investigator's Brochure](#) for references and further details). CR845 was designed to activate KORs located primarily in the peripheral nervous system, which are known to modulate itch, pain, and inflammatory signals, without producing the side effects associated with the activation of mu-opioid receptors, such as respiratory depression, abuse liability, and constipation.

CR845 is a potent and selective KOR agonist with no activity at mu- and delta-opioid receptors or other receptors, ion channels, or transporters. CR845's unique peptidic structure significantly differs from other small molecule KOR agonists developed to date, which, for the most part, are CNS-active. Being a hydrophilic peptide, CR845 has limited membrane permeability by passive diffusion, which limits its access to the CNS. Since CR845 does not activate receptors other than KORs and does not readily enter the CNS, it is expected to be safer and better tolerated than other opioid agonists, including kappa agonists.

Uremic pruritus is a chronic, unremitting, and highly bothersome condition in patients with chronic kidney disease that adversely affects sleep, mood, and ability to socialize [[Kumagai 2010](#)]. Patients with uremic pruritus frequently exhibit considerable mechanical skin damage because of continuous scratching with excoriations, superimposed infections, and chronic lesions of prurigo nodularis or skin lichenification often occurring. The mechanical skin damage can become an additional source of itching. Consequently, these patients are at increased risk of related morbidities associated with infection, eg, cellulitis, sepsis, bacteremia, cutaneous infections, and infections of the dialysis access, and are at higher mortality risk (>15%) [[Pisoni 2006](#); [Narita 2006](#)]. Large multinational studies (Dialysis Outcomes and Practice Patterns) and studies based in the United States have demonstrated that approximately 30 to 40% of hemodialysis patients have moderate-to-severe pruritus. There are no approved treatments for this condition in the United States and current off-label therapies are unable to successfully treat uremic pruritus.

Although the pathophysiology of moderate-to-severe pruritus in hemodialysis patients is not well understood, there is increasing evidence that it is likely multifactorial and that an immune system dysfunction (including elevated proinflammatory activity) and imbalance

in the endogenous opioid system (with over-expression of mu-opioid receptors in dermal cells and lymphocytes and concomitant downregulation of KORs) are involved [Kimmel 2006; Narita 2006; Phan 2012; Patel 2007; Mettang 2002; Tey 2011].

Based on nonclinical pharmacological studies, it was anticipated that CR845 will produce a combined anti-itch, and anti-inflammatory effect (see [Investigator's Brochure](#) for details), which could provide significant relief of itch in hemodialysis patients.

In nonclinical studies, CR845 has been shown to exhibit antipruritic and anti-inflammatory properties [[Investigator's Brochure](#)]. Thus, CR845 is intended to reduce the severity of itching in hemodialysis patients and thereby decrease the likelihood of developing additional serious conditions associated with uremic pruritus.

4.2 Clinical Experience

4.2.1 Overall Exposure

As of the writing of this protocol, the intravenous (IV) formulation of CR845 has been evaluated in 722 patients and healthy volunteers across eight Phase 1 studies (including 2 studies conducted in Japan), three Phase 2 studies for the relief of moderate-to-severe, acute postoperative pain, and two Phase 2 studies for the relief of moderate-to-severe pruritus in hemodialysis patients. In the United States, CR845 has been evaluated both as an IV bolus and a 15-minute infusion of single or repeated doses ranging from 0.5 to 40 mcg/kg.

Of the patients exposed to IV CR845 to date, 213 hemodialysis patients (127 males and 86 females) have received single or repeated IV injections of CR845 doses (for up to 8 weeks) ranging from 0.5 to 6 mcg/kg across two Phase 1 studies and two Phase 2 safety and efficacy studies.

The most current information is contained in the current [Investigator's Brochure](#).

